1. INTRODUCTION

1.1. Indication

The respiratory syncytial virus (RSV) stabilized prefusion F subunit vaccine (RSV vaccine) is being developed for the following indication:

- Prevention of RSV-associated moderate to severe lower respiratory tract disease in adults 60 years of age and older via active immunization.

1.2. Background and Rationale

Human respiratory syncytial virus (HRSV) is the type species of the genus *Pneumovirus*, subfamily Pneumovirinae, family Paramyxoviridae, order Mononegavirales. HRSV exists as 2 antigenic subgroups, A and B, which exhibit genome-wide sequence divergence. RSV is a global pathogen, causing yearly wintertime epidemics in temperate climates, usually between late fall and early spring, lasting 3 to 4 months in a community. In tropical climates, there is no distinct seasonality and outbreaks are more unpredictable, continuous, and generally associated with rainy seasons.¹

Since its identification in 1956, RSV has consistently been noted as the single most important cause of lower respiratory tract infection (LRTI) in infants <1 year of age worldwide. RSV is most notably associated with signs and symptoms of increased airway resistance manifested as wheezing and, in the young child, diagnosed as bronchiolitis. The acute illness usually lasts about 5 to 10 days, but the cough may be prolonged for several weeks.¹ Globally, the incidence of RSV-associated acute LRTI was estimated in 2015 to be approximately 33 million episodes in children younger than 5 years, which resulted in about 3.2 million hospital admissions and about 59,600 hospital deaths. In children younger than 6 months, it is estimated that globally approximately 1.4 million hospital admissions, and approximately 27,300 hospital deaths, were due to RSV-associated acute LRTI.²

RSV is increasingly recognized as an important cause of severe respiratory disease in adults 60 years of age or older as well as individuals with underlying cardiopulmonary and immunocompromised conditions.¹ The clinical presentation of RSV in older adults is not distinctive, and more severe illness is often diagnosed as exacerbation of comorbid conditions, such as chronic obstructive pulmonary disease (COPD) and congestive heart failure.¹ It is estimated that between 11,000 and 17,000 adults die of RSV infection annually in the United States, with approximately 10-fold more admitted to hospital with respiratory symptoms.³ In a US study, it was estimated that the yearly rate of RSV hospitalization among persons 50 to 64 years old was 0.82/1000, and among persons ≥65 years of age it was 2.5/1000.⁴

Currently, there is no vaccine to protect against RSV disease. Treatment consists primarily of supportive care. There is, however, a prophylactic humanized monoclonal antibody against the RSV fusion (F) glycoprotein, palivizumab (Synagis, AstraZeneca), with demonstrated safety and efficacy against severe RSV disease in young infants.^{5,6}

The antibody is costly, requires multiple monthly injections, and is recommended for use only in high-risk and premature infants.⁶ The protective effect of Synagis is definitive proof of concept that serum neutralizing antibody directed against the F protein can provide clinically meaningful protection against RSV lower respiratory tract disease in young infants.

Pfizer is developing a vaccine for the prevention of RSV-associated LRTI, in order to protect infants by maternal immunization during pregnancy, and adults 60 years of age and older via direct immunization.

The aim of RSV vaccination in adults 60 years of age and over is to boost the immune response sufficiently to protect against RSV disease before each RSV season. After RSV natural infection, there is only a relatively short duration of immunity.¹ Serum neutralizing antibody titers in RSV-infected patients who were hospitalized compared with nonhospitalized infected persons suggest that more severe RSV disease is associated with low serum neutralizing antibody.⁷ Additional immune mechanisms may also aid in protection, but the existing evidence supports an important role for serum neutralizing antibody titers in reducing the risk of RSV disease in older adults.

CCI [REDACTED]

[REDACTED]

[REDACTED]

Because immunosenescence⁸ could pose a barrier to effective immunization of the elderly against RSV, there is concern that despite findings in animals suggesting that Al(OH)₃ improves the immune response to the vaccine, the addition of Al(OH)₃ alone may not be sufficient to optimize responses in the elderly, who are at significant risk from RSV disease.

In this study in older adults 65 to 85 years of age, a CpG with aluminum hydroxide (CpG/Al(OH)₃)-adjuvanted formulation, given as a single dose or in a 2-dose regimen administered 2 months apart, will be investigated to assess if the addition of CpG could further improve neutralizing antibody levels relative to formulations with or without Al(OH)₃ at the same dose levels used in the FIH study. In this event, a CpG/Al(OH)₃-adjuvanted formulation would be included in further development studies. CpG is a Toll-like receptor 9 (TLR9) agonist that has been generally well tolerated in human clinical trials for infectious disease indications, such as hepatitis B, malaria, and influenza.⁹ A CpG-containing hepatitis B vaccine, Heplisav-B, was recently licensed in the United States.¹⁰ CCI

Additionally, it is anticipated that an RSV vaccine would optimally be given at the same time as a seasonal influenza vaccine, to facilitate its use in the older adult population. Therefore, this study will assess any potential impact on safety, tolerability, and immune responses to the seasonal inactivated influenza vaccine (SIIV) when the RSV vaccine and SIIV are given concomitantly; similar assessments of concomitant administration of influenza vaccine and RSV vaccine with or without Al(OH)₃ are being conducted in the C3671001 study.

Data from the C3671001 study at 1 month after administration of the 3 dose levels of RSV vaccine (60 µg, 120 µg, and 240 µg), with or without Al(OH)₃ in subjects aged 18 to 85 years, have shown the vaccine is well tolerated and immunogenic, with a trend toward greater immunogenicity at the 240-µg dose level.

The C3671002 study was initiated under protocol Amendment 2 during the southern hemisphere influenza season; however, a delay in SIIV availability prevented the completion of enrollment of the original cohort. Consequently, only 250 subjects of the planned 312 subjects were enrolled. In Amendment 3, this cohort will be referred to as the Primary Study Cohort - Stage 1.

Protocol Amendment 3 will address 2 broad goals:

1. Evaluate a 2-dose regimen administered 2 months apart to determine whether a short dosing interval elicits an enhanced immune response.

Due to the deficit in the originally planned subject enrollment, approximately 62 subjects aged 65-85 years will be randomized 1:1 to receive a dose of 240 µg RSV vaccine with CpG/Al(OH)₃ or placebo followed by a second dose 2 months later. Safety, tolerability, and immunogenicity will be evaluated. This cohort will be known as the RSV Vaccine Month-0, Month-2 Cohort. The subjects will be enrolled before the influenza season. There will be no concomitant SIIV administration.

2. Evaluate safety and immunogenicity of a second dose of RSV vaccine administered to the Primary Study Cohort - Stage 1 subjects, 12 months after the initial dose to determine whether the immune response supports annual vaccination.

The safety and immunogenicity data from C3671001 and Stage 1 of C3671002 will guide the decision on whether a second dose of the RSV vaccine will be evaluated in Stage 2. If Stage 2 proceeds, this cohort will be known as the Primary Study Cohort - Stage 2. If there are no substantial differences in immune responses between the CpG/Al(OH)₃ and Al(OH)₃ formulations, then development of the CpG/Al(OH)₃ formulation may cease, and Stage 2 will not proceed.

If the data support implementation of Stage 2, invited, consenting subjects will be revaccinated with the same dose and formulation of the RSV vaccine or placebo received at Visit 1, concomitantly with SIIV. The safety, tolerability, and immunogenicity of the second dose will be evaluated through 12 months after revaccination.

Additional information for this compound may be found in the single reference safety document (SRSD), which for this study is the investigator's brochure. The SRSD for the SIIV will be the product information for the country where the vaccine was procured.

2. STUDY OBJECTIVES AND ENDPOINTS

Primary Objective:	Primary Endpoints:

Primary Study Cohort - Stage 1:
 
To describe the safety and tolerability of an adjuvanted RSV vaccine given concomitantly with SIIV.
	
Primary Study Cohort - Stage 1:
 
 • Local reactions within 14 days after Vaccination 1. • Systemic events within 14 days after Vaccination 1. • Adverse events (AEs) within 1 month after Vaccination 1. • Medically attended AEs and serious adverse events (SAEs) through 12 months after Vaccination 1 (from Visit 1 through Visit 5).
Secondary Objectives:	Secondary Endpoints:

Primary Study Cohort - Stage 1:
 
To describe the immune responses elicited by an adjuvanted RSV vaccine given with SIIV.
 
To describe the immune responses elicited by SIIV given alone or with an adjuvanted or unadjuvanted RSV vaccine.
	
Primary Study Cohort - Stage 1:
 
 • RSV A– and RSV B–neutralizing antibody titers measured before and 1 month after Vaccination 1. • Hemagglutination inhibition assay (HAI) titers for all strains in the SIIV measured before and 1 month after Vaccination 1.
Exploratory Objectives:	Exploratory Endpoints:

Primary Study Cohort - Stage 1:
 
To more fully characterize the immune response to an adjuvanted RSV vaccine and to any concurrent RSV infection.
 
To more fully characterize the immune response to SIIV.
	
Primary Study Cohort - Stage 1:
 
 • RSV A– and RSV B–neutralizing antibody titers measured at 1 week (peripheral blood mononuclear cell [PBMC] subjects) and 3, 6, and 12 months after Vaccination 1. • Plasmablast frequencies and T-cell phenotype and functional analysis before and 1 week after Vaccination 1 (PBMC subjects). • Memory B-cell and T-cell frequencies and their functional analysis before vaccination, and 1 and 6 months after Vaccination 1. • Immunoglobulin G (IgG) titers against prefusion F before vaccination, and 1, 3, 6, and 12 months after Vaccination 1. • IgG titers to nonvaccine RSV antigens before vaccination, and 1, 3, 6, and 12 months after Vaccination 1. • H3N2-neutralizing antibody titers measured before vaccination and 1 month after Vaccination 1.


Primary Study Cohort - Stage 2:
 
To describe the safety and tolerability of a second dose of adjuvanted RSV vaccine given concomitantly with SIIV.
 
To describe the immune responses elicited by a second dose of an adjuvanted RSV vaccine given concomitantly with SIIV.
 
To more fully characterize the immune response to SIIV when given concomitantly with a second dose of RSV.
	
Primary Study Cohort - Stage 2:
 
 • Local reactions within 14 days after Vaccination 2. • Systemic events within 14 days after Vaccination 2. • AEs within 1 month after Vaccination 2. • Medically attended AEs and SAEs through 12 months after Vaccination 2. • RSV A– and RSV B–neutralizing antibody titers measured at 1 week (PBMC subjects) and 1, 3, 6, and 12 months after Vaccination 2. • Plasmablast frequencies and T-cell phenotype and functional analysis before Vaccination 2 and 1 week after Vaccination 2 (PBMC subjects). • Memory B-cell and T-cell frequencies and their functional analysis before Vaccination 2, and 1 and 6 months after Vaccination 2. • IgG titers against prefusion F before Vaccination 2, and 1, 3, 6, and 12 months after Vaccination 2. • IgG titers to nonvaccine RSV antigens before Vaccination 2, and 1, 3, 6, and 12 months after Vaccination 2. • HAI titers for all strains in the SIIV measured before and 1 month after Vaccination 2. • H3N2-neutralizing antibody titers measured before Vaccination 2 and 1 month after Vaccination 2.

RSV Vaccine Month-0, Month-2 Cohort
 
To describe the safety and tolerability of the first and second dose of an adjuvanted RSV vaccine administered 2 months apart.
 
To describe the immune responses elicited by the first and second dose of adjuvanted RSV vaccine administered 2 months apart.
	
RSV Vaccine Month-0, Month-2 Cohort
 
 • Local reactions within 14 days after Vaccinations 1 and 2. • Systemic events within 14 days after Vaccinations 1 and 2. • AEs within 1 month after Vaccinations 1 and 2. • AEs from Vaccination 1 through 1 month after Vaccination 2. • Medically attended AEs and SAEs through 12 months after Vaccination 2. • RSV A– and RSV B–neutralizing antibody titers measured at scheduled timepoints before and after each vaccination scheduled. • Plasmablast frequencies and T-cell phenotype and functional analysis before each vaccination and 1 week after Vaccinations 1 and 2 (PBMC subjects). • Memory B-cell and T-cell frequencies and their functional analysis before each vaccination, and 1 and 6 months after Vaccinations 1 and 2. • IgG titers against prefusion F at scheduled timepoints before and after each vaccination. • IgG titers to nonvaccine RSV antigens at scheduled timepoints before and after each vaccination.

3. STUDY DESIGN

This is a Phase 1/2, multicenter, randomized, placebo-controlled, observer-blind, dose- and formulation-finding study to describe the safety, tolerability, and immunogenicity of up to 7 different RSV vaccine candidates with bivalent formulations (RSV A and RSV B) at 3 dose levels of 60 µg of the prefusion RSV F antigens [REDACTED] 120 µg [REDACTED] and 240 µg [REDACTED] formulated with aluminum hydroxide (Al(OH)₃) or CpG/Al(OH)₃, or a 240 µg RSV vaccine [REDACTED] alone, when administered concomitantly with SIIV, or without SIIV in a Month-0 and Month-2 schedule.

The dose for the RSV vaccine alone was selected based on 1-month postvaccination immunogenicity data from the sentinel-cohort subjects in Study C3671001 (A Phase 1/2, Placebo-Controlled, Randomized, Observer-Blind, Dose-Finding, First-in-Human Study to Describe the Safety, Tolerability, and Immunogenicity of a Respiratory Syncytial Virus (RSV) Vaccine in Healthy Adults; ClinicalTrials.gov identifier: NCT03529773).

The study is organized in the following cohorts:

1. Primary Study Cohort - Stage 1, will evaluate RSV vaccine doses/formulations given concomitantly with SIIV at Month 0.
2. Primary Study Cohort - Stage 2, will evaluate revaccination of the Stage 1 subjects with a RSV vaccine and concomitant SIIV, administered at Month 12.
3. RSV Vaccine Month-0, Month-2 Cohort will evaluate a 240 µg dose of RSV vaccine with CpG/Al(OH)₃ given at Months 0 and 2. No concomitant SIIV will be given.

Male and female subjects 65 to 85 years of age will be enrolled. Subjects will be randomized equally across all dose groups in the primary cohorts. The RSV Vaccine Month-0, Month-2 Cohort will be randomized 1:1 to receive RSV vaccine or placebo.

Primary Study Cohort - Stage 1

Enrollment in the Primary Study Cohort - Stage 1 commenced in April 2019 and completed enrollment in June 2019. Approximately 250 subjects 65 to 85 years of age received 2 intramuscular injections at Visit 1 to assess the concomitant administration of SIIV when given to subjects receiving one of the 3 RSV vaccine dose-level candidates formulated with Al(OH)₃ or CpG/Al(OH)₃ or the RSV vaccine-alone dose (see [Section 6.1](#) for further details).

The first 4 subjects vaccinated in the study were observed by blinded site staff for any acute reactions for at least 4 hours after vaccination. Vaccination of the remaining subjects commenced no sooner than 48 hours after the fourth subject received his or her vaccination. Vaccination of subjects was limited to a maximum of 6 subjects per day during the first week of enrollment (up to 30 vaccinated subjects in total). Follow-up will continue through Month 12.

Primary Study Cohort - Stage 2

Prior to completion of Stage 1, subjects may be invited to participate in Stage 2. Safety and immunogenicity data obtained from the C3671001 and C3671002 studies will be used to determine whether Stage 2 will proceed and, if so, whether all or some of the RSV formulations will be evaluated.

If the data support implementation of Stage 2, consenting subjects will be revaccinated with the same dose and formulation of the RSV vaccine or placebo received at Visit 1, concomitantly with SIIV. The safety, tolerability, and immunogenicity of the second dose will be evaluated through 12 months after revaccination.

If the data do not support the implementation of revaccination at 12 months, Stage 2 will not proceed.

RSV Vaccine Month-0, Month-2 Cohort

Approximately 62 RSV vaccine-naïve subjects will be randomized 1:1 to receive either 240 µg of RSV vaccine with CpG/Al(OH)₃ or placebo at Visit 1 (Month 0). At Visit 3 (Month 2), subjects will receive a second dose of RSV vaccine or placebo as randomized at Visit 1. No concomitant SIIV will be given.

In Stage 1, the 240-µg dose for the nonadjuvanted RSV vaccine was selected based on the 1-month postvaccination immunogenicity data from the sentinel-cohort subjects in Study C3671001. The same dose will be used for the RSV Vaccine Month-0, Month-2 Cohort.

An internal review committee (IRC) and an external data monitoring committee (E-DMC) will monitor safety in this study (refer to [Section 9.5](#)).

3.1. Number of Subjects

In total, approximately 312 subjects will be randomized to receive RSV vaccine at different dose levels and formulations or placebo at different vaccination schedules. Approximately 250 subjects were enrolled in the Primary Study Cohort - Stage 1 and approximately 62 RSV vaccine-naïve subjects will be enrolled in the RSV Vaccine Month-0, Month-2 Cohort (see [Table 4](#) below). Of these, a subset of subjects in all cohorts will be included in the whole blood collection procedural requirements for the exploratory cellular analysis endpoints for this study. The subset will be determined at the site level. Those sites that have access to the appropriate specimen-processing laboratories will provide all subjects for the PBMC collection subset. It is anticipated that the subjects from the selected sites will constitute approximately 1/3 of the total number of randomized subjects.

Subjects who withdraw or are withdrawn from the study after randomization will not be replaced, regardless of the reason for withdrawal.

Table 4. Randomization of Subjects by Dose and Formulation

Primary Study Cohort			Approximate Number of Males and Females 65 to 85 Years of Age	
Dose/Formulation		Stage 1 / Stage 2	Originally Planned Study Target	Vaccinated in Stage 1
60 µg	RSV+Al(OH) ₃ SIIV	(Month 0/Month 12 ^a)	39	~31 ^b
	RSV+CpG/Al(OH) ₃ SIIV	(Month 0/Month 12 ^a)	39	~31 ^b
120 µg	RSV+Al(OH) ₃ SIIV	(Month 0/Month 12 ^a)	39	~31 ^b
	RSV+CpG/Al(OH) ₃ SIIV	(Month 0/Month 12 ^a)	39	~31 ^b
240 µg	RSV+Al(OH) ₃ SIIV	(Month 0/Month 12 ^a)	39	~31 ^b
	RSV+CpG/Al(OH) ₃ SIIV	(Month 0/Month 12 ^a)	39	~31 ^b
240 µg	RSV SIIV	(Month 0/Month 12 ^a)	39	~31 ^b
	Placebo SIIV	(Month 0/Month 12 ^a)	39	~31 ^b
Total			312	250
RSV Vaccine Month-0, Month-2 Cohort			Target	
240 µg	RSV+CpG/Al(OH) ₃	(Month 0/Month 2)	31	
	Placebo	(Month 0/Month 2)	31	
Total			62	
Total study size			312	

Abbreviations: Al(OH)₃ = aluminum hydroxide; RSV = respiratory syncytial virus vaccine; SIIV = seasonal inactivated influenza vaccine.

- Primary Study Cohort - Stage 2 is contingent on supporting data from Stage 1 and applies to invited/consenting subjects only.
- Approximate number of subjects vaccinated in each dose/formulation group are shown, actual numbers per group will be known after unblinding.

3.2. Duration of Subject Participation

Subjects enrolled in the Primary Study Cohort - Stage 1 will participate in the study for approximately 12 months, or up to approximately 24 months if completing Stage 2.

Subjects enrolled in the RSV Vaccine Month-0, Month-2 Cohort will participate in the study for approximately 14 months.

3.3. Duration of Study

The study will last approximately 26 months.

The study is dependent on SIV availability and access to subjects who have not received SIV within the preceding 6 months. It is anticipated that the study will be conducted in the same geographic location; however, if required for operational reasons, this study may be conducted in more than 1 geographic location over more than 1 influenza season.

4. SUBJECT ELIGIBILITY CRITERIA

This study can fulfill its objectives only if appropriate subjects are enrolled. The following eligibility criteria are designed to select subjects for whom participation in the study is considered appropriate. All relevant medical and nonmedical conditions should be taken into consideration when deciding whether a particular subject is suitable for this protocol.

Subject eligibility should be reviewed and documented by an appropriate member of the investigator's study team before subjects are included in the study.

4.1. Inclusion Criteria

Subjects must meet all of the following inclusion criteria to be eligible for enrollment into the study:

1. Evidence of a personally signed and dated informed consent document (ICD) indicating that the subject has been informed of all pertinent aspects of the study.
2. Healthy adults who are determined by medical history, physical examination, and clinical judgment of the investigator to be eligible for inclusion in the study.

Note: Healthy subjects with preexisting stable disease, defined as disease not requiring significant change in therapy or hospitalization for worsening disease within 6 weeks before enrollment, can be included.

3. Willing and able to comply with scheduled visits, vaccination plan, laboratory tests, and other study procedures.
4. Male and nonchildbearing-potential female adults 65 to 85 years of age at the time of enrollment (signing of the ICD).

Note: Female subjects of nonchildbearing potential must meet at least 1 of the following criteria:

- Postmenopausal status, defined as follows: cessation of regular menses for at least 12 consecutive months with no alternative pathological or physiological cause; status **may be** confirmed with a serum follicle-stimulating hormone (FSH) level confirming the postmenopausal state;
- Have undergone a documented hysterectomy and/or bilateral oophorectomy;
- Have medically confirmed ovarian failure.

All other female subjects (including female subjects with tubal ligations) are considered to be of childbearing potential.

5. Subjects must have received the primary vaccination (RSV vaccine or placebo) at Visit 1 and have signed and dated the ICD for participating in the revaccination stage (applies to Primary Study Cohort - Stage 2 subjects).

4.2. Exclusion Criteria

Subjects with any of the following characteristics/conditions will not be included in the study:

1. Investigator site staff members directly involved in the conduct of the study and their family members, site staff members otherwise supervised by the investigator, or subjects who are Pfizer employees, including their family members, directly involved in the conduct of the study.
2. Participation in other studies involving investigational product within 28 days prior to study entry and/or during study participation.
3. Known infection with human immunodeficiency virus (HIV), hepatitis C virus (HCV), or hepatitis B virus (HBV).
4. Previous vaccination with any licensed or investigational RSV vaccine before enrollment into the study, or planned receipt throughout the study of nonstudy RSV vaccine
5. Vaccination with any influenza vaccine within 6 months (182 days) before investigational product administration (applies to Primary Study Cohort - Stages 1 and 2).
6. History of severe adverse reaction associated with a vaccine and/or severe allergic reaction (eg, anaphylaxis) to any component of the investigational product(s), including natural rubber latex. In addition, a history of severe allergic reaction (eg, anaphylaxis) to any substance, including documented allergy to egg proteins (egg or egg products) or chicken proteins.

7. Subjects with known or suspected immunodeficiency, as determined by history and/or laboratory/physical examination.
8. Subjects receiving treatment with immunosuppressive therapy, including cytotoxic agents or systemic corticosteroids, eg, for cancer or an autoimmune disease, or planned receipt throughout the study. If systemic corticosteroids have been administered short term (<14 days) for treatment of an acute illness, subjects should not be enrolled into the study until corticosteroid therapy has been discontinued for at least 28 days before investigational product administration. Inhaled/nebulized, intra-articular, intrabursal, or topical (epidural, skin, or eyes) corticosteroids are permitted.
9. Subjects with a history of autoimmune disease or an active autoimmune disease requiring therapeutic intervention including but not limited to: systemic or cutaneous lupus erythematosus, autoimmune arthritis/rheumatoid arthritis, Guillain-Barré syndrome, multiple sclerosis, Sjögren syndrome, idiopathic thrombocytopenic purpura, autoimmune glomerulonephritis, autoimmune thyroiditis, giant cell arteritis (temporal arteritis), psoriasis, and insulin-dependent diabetes mellitus (type 1).
10. Receipt of any blood/plasma products or immunoglobulin, from 60 days before investigational product administration or planned receipt throughout the study.
11. Bleeding diathesis or condition associated with prolonged bleeding that would, in the opinion of the investigator, contraindicate intramuscular injection.
12. Female subjects of childbearing potential or who are pregnant or breastfeeding; fertile male subjects who are unwilling to use a highly effective method of contraception for at least 28 days after the last dose of investigational product.
13. Other acute or chronic medical or psychiatric condition including recent (within the past year) or active suicidal ideation or behavior or laboratory abnormality that may increase the risk associated with study participation or investigational product administration or may interfere with the interpretation of study results and, in the judgment of the investigator, would make the subject inappropriate for entry into this study.
14. Planned donation of blood volumes of approximately 470 mL within 12 weeks after Vaccination 1 (applies to subjects having additional blood drawn for cellular assays).

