Document	Version Date	Summary of Changes and Rationale
		
footer.
 
Section 4: Added inclusion criterion 5. Modified exclusion criteria 4 and 5 to reflect the new design. Added exclusion criterion 14 so that elderly subjects are not compromised due to frequent blood draws.
 
Section 5.1.2: Modified blinding text in line with the new design.
 
Section 5.4.1.1 and Table 5: Replaced “TBD” with the RSV vaccine dose.
 
Section 5.5: Modified the vaccine administration text to describe the timing of vaccinations by cohort. Table 6: Added administration information by cohort.
 
Section 5.8.2: Added a statement regarding the exclusionary period for the influenza vaccine for the Stage 2 cohort.
 
Section 5.8.3: Added applicability text for the administration of the influenza vaccine. Added a statement on the timing of the administration of the influenza vaccine for the RSV Month-0, Month-2 Cohort.
 
Section 6: Added text to note that Section 6.1 applies to the Primary Study Cohort - Stage 1. Added text to emphasize that blood samples for cellular assays apply to consenting PBMC subjects at PBMC collection sites only.
 
Section 6.2: Added a detailed visit schedule for the Primary Study Cohort - Stage 2.
 
Section 6.3: Added a detailed visit schedule for the RSV Vaccine Month-0,

Document	Version Date	Summary of Changes and Rationale
		
Month-2 Cohort.
 
Section 7.2: Modified the immunogenicity blood sample collection to reflect sampling by study cohort.
 
Section 7.3: Moved the text into a logical order based on the new design. Made slight modifications to text based on the new design.
 
Section 8.1.4: Clarified the text to emphasize the adverse event (AE) collection periods based on the modified vaccination schedules.
 
Section 9: Modified the sample size determination by study cohort. Modified the probability table based on the new subject numbers per cohort.
 
Section 9.2: Modified study populations to reflect the new design.
 
Section 9.4: Modified text to show that 3 interim analyses will be performed. Text includes timing relative to vaccination and data to be analyzed.
 
Section 9.5: Removed redundant text regarding the timing of the data monitoring committee (DMC) review as details are addressed in the DMC charter.
 
Throughout: Made minor editorial revisions as appropriate.

Document	Version Date	Summary of Changes and Rationale

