- c. This blood collection is only applicable to subjects consenting to PBMC collection at designated PBMC sites.

Table 2 Primary Study Cohort - Stage 2 Schedule of Activities is applicable to Stage 1 subjects who are invited and consent to revaccination at Month 12. Study procedures for this cohort are fully described in [Section 6.2](#).

Table 2. Schedule of Activities: Primary Study Cohort - Stage 2						
Visit Number	5^a	6A^b	6	7	8	9
Visit Description	Vaccination 2	1-Week Revaccination Follow-up Visit	1-Month Revaccination Follow-up Visit	3-Month Revaccination Follow-up Visit	6-Month Revaccination Follow-up Visit	12-Month Revaccination Follow-up Visit
Study Period	Month 12		Month 13	Month 15	Month 18	Month 24
Visit Window (Days)	300 to 400 Days after Visit 1	6 to 8 Days After Visit 5	28 to 35 Days After Visit 5	84 to 105 Days After Visit 5	168 to 210 Days After Visit 5	350 to 378 Days After Visit 5
Confirm/obtain informed consent for Stage 2 ^c	X					
Perform physical examination, vital signs (weight, oral temperature, heart rate, and seated blood pressure)	X					
Review inclusion/exclusion criteria	X					
Record nonstudy vaccine information	X	X	X	X	X	X
Review temporary delay criteria	X					
Confirm understanding and compliance with protocol requirements for contraception (male subjects)	X	X	X			
Obtain IP container number	X					
Collect blood sample for antibody assessment	~25 mL		~25 mL	~25 mL	~25 mL	~25 mL
Collect blood sample for cellular assay ^d	~100 mL	~50 mL	~50 mL		~50 mL	
Administer investigational product in left deltoid muscle and SIIV in right deltoid muscle	X					
Assess acute reactions for at least 30 minutes after investigational product administration	X					
Provide subject with 14-day e-diary, thermometer, and measuring device	X					
Review e-diary data (daily review is optimal)	-----X-----					

Table 2. Schedule of Activities: Primary Study Cohort - Stage 2

Visit Number	5 ^a	6A ^b	6	7	8	9
Visit Description	Vaccination 2	1-Week Revaccination Follow-up Visit	1-Month Revaccination Follow-up Visit	3-Month Revaccination Follow-up Visit	6-Month Revaccination Follow-up Visit	12-Month Revaccination Follow-up Visit
Study Period	Month 12		Month 13	Month 15	Month 18	Month 24
Visit Window (Days)	300 to 400 Days after Visit 1	6 to 8 Days After Visit 5	28 to 35 Days After Visit 5	84 to 105 Days After Visit 5	168 to 210 Days After Visit 5	350 to 378 Days After Visit 5
during the active diary period)	14 days					

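### Exclusion criterion 14 bars a planned blood donation only after Vaccination 1, so it has no effect at the Stage 2 eligibility check; a one-phrase addition would close this minor gap

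*Protocol*

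**What the plan says.** Criterion 14 in Protocol Section 4.2, repeated in the Protocol Summary, excludes subjects with "Planned donation of blood volumes of approximately 470 mL within 12 weeks after Vaccination 1". Its scope is set by a parenthesis: it "applies to subjects having additional blood drawn for cellular assays". Section 3.1 says that "a subset of subjects in all cohorts will be included in the whole blood collection procedural requirements", and that subjects at the selected sites "will constitute approximately 1/3 of the total number of randomized subjects".

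The summary of changes, used here only as evidence of intent, gives the reason: "Added exclusion criterion 14 so that elderly subjects are not compromised due to frequent blood draws". For the same amendment it also lists "Modified exclusion criteria 4 and 5 to reflect the new design" and "Added a detailed visit schedule for the Primary Study Cohort - Stage 2".

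Table 2 labels Visit 5 of Stage 2 as Vaccination 2, places it 300 to 400 days after Visit 1, and lists "Review inclusion/exclusion criteria" among that visit's activities. Section 6.2.1 requires site staff to document the outcome of that check before vaccination.

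**The concern.** The criterion is tied to Vaccination 1, while Stage 2 begins about a year later with its own vaccination, its own eligibility check and its own series of PBMC draws. If the bar is meant to stop a voluntary donation being added to a run of study draws in people aged 65 to 85, one would expect it to apply to Stage 2 as well.

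Stage 1 finished enrolling in June 2019 and the amendment is dated 22 August 2019, so the criterion could not have screened Primary Study Cohort subjects at Visit 1 either. Visit 5 is the only remaining point at which it could act for them.

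What is at stake is subject protection. No endpoint, population or estimate depends on it.

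**Working it through.** **Inputs.** The criterion 14 period is 12 weeks after Vaccination 1 (Section 4.2). Visit windows and draw volumes come from Tables 1 to 3 and Sections 6.1 to 6.3. Stated totals are in Section 7.2.

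**1. Reproduce the plan's Stage 2 total.**
- Antibody draws at Visits 5, 6, 7, 8 and 9: 5 × 25 = 125 mL.
- Cellular draws at Visits 5, 6A, 6 and 8: 100 + 50 + 50 + 50 = 250 mL.
- Sum: 125 + 250 = 375 mL, which agrees with Section 7.2.

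**2. Compare the period with Visit 5.**
- End of the period: 12 × 7 = day 84.
- Gap to Visit 5: 300 − 84 = 216 days at the least, 400 − 84 = 316 days at the most.
- The period has closed long before the Stage 2 check.

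**3. Stage 2 PBMC volume soon after Visit 5.**
- Visit 5: 25 + 100 = 125 mL.
- Visit 6A (6 to 8 days later): 50 mL.
- Visit 6 (28 to 35 days later): 25 + 50 = 75 mL.
- Sum: 125 + 50 + 75 = 250 mL by day 35, or 250/375 = 67% of the Stage 2 total. It consists of 50 mL antibody and 200 mL cellular blood, and equals the cellular total in step 1 only by coincidence.
- With a 470 mL donation in the same 12 weeks: 250 + 470 = 720 mL. If Visit 7 (25 mL) falls on day 84: 745 mL.

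**4. The other cohorts, PBMC subjects.**
- Month-0, Month-2 Cohort by day 35: 125 + 50 + 75 = 250 mL, the same as Stage 2.
- That cohort by Visit 4A (day 60 to 74): 250 + 75 + 50 = 375 mL. Visit 4 can fall as early as day 54 + 28 = 82, which gives 375 + 75 = 450 mL inside the 12 weeks.
- Stage 1 by day 35: 150 + 100 + 100 = 350 mL, drawn before the criterion existed.

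**5. Other limits on donation.** The delay criteria (4.3), the lifestyle section (4.4, contraception only) and the concomitant-treatment rules (5.8) do not mention donation. Exclusion criterion 13 concerns a medical or psychiatric condition or a laboratory abnormality, and a planned donation is neither.

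**6. Reach.** If one third of the 250 Stage 1 subjects are in the PBMC subset and all continue, 250/3 = about 83. The share planning a donation is not given. An assumed 1% gives 0.8, 5% gives 4.2 and 10% gives 8.3 subjects.

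**The case against.** The strongest reply is that the anchor was chosen on purpose. When the criterion was added, the Month-0, Month-2 Cohort was the only group with Vaccination 1 still ahead. Twelve weeks fits its schedule: five or six draws and 375 to 450 mL fall inside. Stage 2 has three draws and 250 mL in the same span, plus Visit 7 only if that lands on day 84. The stated purpose concerns frequent draws, and Stage 2 has fewer. The same list of criteria extends a restriction over the whole study, to the last dose or to named stages where that is intended, so naming Vaccination 1 may be deliberate. Nor must every criterion exclude someone at a re-check: inclusion criterion 4 is fixed at enrollment.

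Much of this stands. It explains the wording plausibly, and it shows that Stage 2 is the lighter schedule over 12 weeks. It does not supply a donation limit for Stage 2. Nor does criterion 14 confine itself to one cohort, as inclusion criterion 5 and exclusion criterion 5 do by naming theirs; it names the cellular-assay subset, which exists in every cohort.

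A reader might also infer that investigator judgment is all that protects Stage 2 subjects. The protocol does not support that. Stage 2 has separate written consent, a physical examination with vital signs at Visit 5, recording of any AE up to 48 hours after blood draws, and withdrawal for safety. The consent pages are not in the text available, so whether they advise on donation is unknown. None of the visible safeguards is a donation bar, but they are more than judgment alone.

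**Conclusion.** The point holds as a minor, cheap improvement. Criterion 14 cannot act at the Stage 2 check, and the visible protocol puts nothing specific in its place. The early draw volume is the same 250 mL in 35 days as in the cohort where the bar does work.

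Two stronger readings go beyond the documents. One is that a Vaccination 2 anchor was left out by mistake: the documents do not state the intended scope for Stage 2, so this is inference. The other is that the gap exposes subjects to an unsafe volume: the documents give no such threshold, and Stage 1 took 350 mL over the same interval.

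The figure of about 83 subjects is an upper limit. The range of about 1 to 8 who might plan a donation rests wholly on the assumed 1% to 10%, and each would still come under the general safeguards. The point matters only if Stage 2 proceeds. SAP Section 2.2 reports that sites were first told all subjects would be revaccinated and then told to postpone. No statistical result changes. Lowest severity.

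**What to change.** In Section 4.2 and the Protocol Summary, add to criterion 14: 'or, for Primary Study Cohort - Stage 2 subjects, within 12 weeks after Vaccination 2'. The check at Visit 5 can then exclude someone, and the bar covers Visits 5, 6A and 6. The period for the Month-0, Month-2 Cohort stays as it is. If the sponsor does not intend Stage 2 to be covered, criterion 14 should name the cohort it applies to.

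The cost is one phrase in two places, with no new visit, procedure or analysis. A few Stage 2 PBMC subjects may have to defer a donation or leave the PBMC subset. Under a 12-week bar, 84 − 35 = 49 to 84 − 28 = 56 days would come after Visit 6, with no draw scheduled until Visit 7 (25 mL, day 84 to 105). Ending the Stage 2 bar at Visit 6 would spare subjects that part and still cover the 250 mL.
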